5.2. Primary Efficacy Outcome

5.2.1. Definition

The primary efficacy outcome is the composite of all symptomatic VTE events (lower extremity DVT, non-fatal PE) and VTE-related death (death due to PE or death in which PE cannot be ruled out as the cause).

5.2.2. Analysis Methods

The primary efficacy outcome will be analyzed based on the time from randomization to the first occurrence of symptomatic VTE and VTE-related death in the ITT analysis set and Up-to-Day-45 analysis phase. The primary statistical hypothesis will be tested using Cox proportional hazards model, stratified by subjects with CrCl from ≥ 30 to < 50 mL/min versus subjects with CrCl ≥ 50 mL/min, with the treatment (as randomized) as the only covariate. Subjects will be analyzed according to the treatment group to which they are randomized, regardless of actual treatment received. As an operational arrangement, the 2-sided p-value will be reported, and if it is less than the 2-sided alpha of 0.05, then superiority of the study drug will be declared when the observed survival functions favor rivaroxaban. Note that the above testing procedure is equivalent to stratified logrank test². The use of the Cox model format facilitates a consistent presentation of tests and CIs from analyses of efficacy and safety outcomes and from subgroup and sensitivity analyses.

The point estimate and corresponding 95% CI for the HR (rivaroxaban to placebo) will be provided based on the Cox proportional hazards model. For the CIs, the plausibility of proportional hazards assumption will be assessed by visually comparing the plot of the log of cumulative hazard between treatments, and additionally checked by adding a treatment by logarithm-transformed time interaction into the Cox model. If there is strong indication that the proportional hazards assumption is not valid, the 95% CI for relative risk of rivaroxaban versus placebo based on the incidence of the primary efficacy outcome from randomization up to Day 45 will be additionally provided, using the Cochran–Mantel–Haenszel (CMH) statistic with stratification by CrCl groups.

The cumulative event rate derived from the Kaplan-Meier method will be displayed graphically to evaluate the treatment effect over time.

The following sensitivity analyses of the primary efficacy outcome will be conducted to assess the robustness of the conclusion from primary efficacy analysis: a) stratified Cox model as in the primary efficacy analysis but additionally stratified by region, b) stratified Cox model as in the primary efficacy analysis but based on the per-protocol analysis set and on-treatment analysis phase. The additional sensitivity analyses of the primary efficacy outcome may be necessary to exclude subjects (e.g., significant quality issues, GCP violations, data integrity issues, regulatory agency commitment). Additional post-hoc analyses may be conducted to investigate unexpected

results. Off-treatment primary efficacy outcome events, defined by the events from the 3 days after the last dose date, will be summarized by treatment groups.

Extensive efforts will be made to collect complete event and vital status data for all subjects randomized in this study. The amount of unavoidable missing follow-up in this study with relatively short treatment duration of 45 days is not expected to influence the conclusion from the efficacy analyses. To illustrate the extent of missingness for the primary efficacy outcome, the numbers of subjects with missing follow-up and the percentages of total missing follow-up time out of total supposed follow-up time will be summarized. A non-completer of the study will be considered as a missing follow-up subject. Missing follow-up time will be calculated by Day 45 date - last outcome-evaluation date for a missing follow-up subject. For a subject, supposed follow-up time will be calculated by minimum of [Day 45 date, death date, first primary efficacy event date] - randomization date +1. Sensitivity analyses will be conducted to estimate any additional events from the rivaroxaban and placebo group during the missing follow-up time that are needed to overturn a superiority conclusion from the primary efficacy analysis. Similar sensitivity analyses may be conducted for each component of the primary efficacy outcome.

Homogeneity of treatment effects, both in HR and direction, in the subgroups defined in section 2.4 will be explored via a test for treatment by subgroup interaction in the stratified Cox model with treatment, subgroup and the treatment-by-subgroup interaction as the covariates, stratified by CrCl group (≥ 30 to < 50 , ≥ 50 mL/min) (at a 2-sided significance level of 0.05). For CrCl subgroups, unstratified Cox model will be used. Lack of a significant interaction will imply that the results are consistent across subgroups. If a significant interaction is observed, the results will be examined to determine whether the interaction is qualitative in nature using Pan and Wolfe approach³ (1997). If the interaction is qualitative in nature, clinical explanations of the significant interaction will be explored.

For each individual subgroup, the estimate and CI for HR will be constructed based on the stratified Cox model except for the CrCl subgroups. If the number of subjects with a primary efficacy outcome in a treatment-by-stratum cell in a subgroup is less than 5, interpretation of the CI needs to be done with caution.

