As described in Section 1.1.5, 3 studies have been conducted testing an extended period of thromboprophylaxis. For each of these studies, a post-hospital discharge placebo comparator was used, and none provided evidence of a benefit/risk balance better than placebo. The MARINER study will enroll a population at greater risk of VTE and lower risk of bleeding than previously studied, and will use the placebo comparator as the standard of care, as recommended by the

ACCP. Given the ACCP guidelines, the duration of thromboprophylaxis in these patients is usually determined by the duration of hospitalization, as it is unusual for patients to receive thromboprophylaxis after discharge. In fact, in the MARINER study, patients for whom thromboprophylaxis is prescribed after discharge are specifically excluded.

Based on the above, placebo has been chosen as the appropriate comparator to allow for the evaluation of benefit/risk of rivaroxaban as thromboprophylactic agent in post-hospital discharge high-risk, medically ill patients.

Any patient with a medical condition that will require chronic use of any parenteral or oral anticoagulation (eg, atrial fibrillation) during the study is not eligible for participation. During the study, should the subject develop any condition, which in the investigator's judgment requires long-term anticoagulation, thromboprophylaxis, or fibrinolysis, the subject will have study treatment either temporarily interrupted or permanently discontinued and will be managed as deemed appropriate by the treating physician. The subject will be asked to continue in the study to be followed for efficacy and safety outcomes.

Dose Selection

The selection of a dose of 10 mg daily of rivaroxaban is based primarily on the results of the studies conducted for prophylaxis of VTEs in patients undergoing knee or hip replacement surgery, where 10 mg daily of rivaroxaban resulted in benefit with an acceptable risk profile.

Subjects with CrCl ≥ 50 mL/min will be randomly assigned to receive rivaroxaban 10 mg daily or placebo. In order to reduce the risk of bleeding in subjects with a baseline CrCl ≥ 30 mL/min and < 50 mL/min (estimated to be approximately 20% of study population), a dose adjustment of rivaroxaban from 10 mg daily to 7.5 mg daily will be implemented (Section 3.1)

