In the ROCKET AF study, a 25% dose reduction of rivaroxaban (15 mg daily) was implemented in subjects with CrCl 30 to 49 mL/min (approximately 20% of the study population), which provided comparable exposure, efficacy and safety to that of rivaroxaban 20 mg daily administered to subjects with CrCl ≥ 50 mL/min²⁹. Since the age and comorbidities of the subjects in the proposed MARINER study are similar to the population studied in the ROCKET AF study and based on the population PK simulations of a virtual medically ill population, a similar 25% dose reduction of rivaroxaban (from 10 mg to 7.5 mg daily) in the subjects with CrCl ≥ 30 mL/min and < 50 mL/min is a reasonable strategy. This rivaroxaban dose reduction in medically ill subjects with CrCl ≥ 30 mL/min and < 50 mL/min is predicted to yield similar rivaroxaban plasma exposures to those in subjects with CrCl ≥ 50 mL/min at a 10 mg dose. Based on the achievement of similar plasma exposures, comparable efficacy and safety would be expected in these 2 population subgroups.

Choice of Efficacy Measure

The choice of the primary efficacy outcome is based on prior rivaroxaban trials for primary and secondary prevention of VTE events (such as DVT, PE) and VTE-related deaths. In addition, these outcomes are considered acceptable and verifiable for the evaluation of prevention of VTE events in medically ill patients^{10,15,18}.

Asymptomatic proximal DVT, as detected on compression ultrasonography, was included as part of the primary efficacy outcome in the 3 extended-duration studies (EXCLAIM, ADOPT and MAGELLaN). Compression ultrasonography is not performed routinely in medical patients and the use of this test might influence the symptomatic VTE component of the primary efficacy composite outcomes¹⁵. Specifically, the performance of compression ultrasound during double-blind treatment likely influences the subsequent natural history of the disease by prompting investigators to treat asymptomatic clots. Therefore, without asymptomatic clot detection there will be a higher symptomatic event rate and assessment of only symptomatic events may provide a more clinically meaningful evaluation of a therapeutic intervention. Thus, in the present study only hard efficacy outcomes (symptomatic VTE events, VTE-related deaths, etc.) will be measured.

Choice of Safety Measures

The principal safety outcome is major bleeding using validated ISTH bleeding criteria.

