1.4. Sample Size Justification

This is an event driven study. The targeted total number of primary efficacy outcome is 161, based on the ITT analysis set and Up-to-Day-45 analysis phase. If a subject has multiple events, only the first is counted towards study size determination.

This targeted total number of events is determined using statistical software East 5.3 based on the primary efficacy analysis (defined later) and the following assumptions:

- 40% relative risk reduction (RRR) in the primary efficacy outcome based on the ITT analysis set and Up-to-Day-45 analysis phase (RRR is defined as 1 minus the hazard ratio (HR) of rivaroxaban versus placebo.)
- Power of 90% assuming the above RRR
- Two-sided significance level of 0.05.

To observe the targeted 161 events, it is estimated that a total of approximately 8,000 subjects will need to be randomized to either rivaroxaban or placebo in 1:1 ratio. This estimate is based on an estimated placebo incidence rate of the primary efficacy outcome of 2.5%. In the event that the actual observed blinded pooled event rate is lower than the assumed rate, more subjects may be enrolled to accumulate additional outcome events. Randomization in this study may be stopped at approximately 12,000 subjects for administrative considerations even if the targeted 161 events have not been observed by then. The total number of VTE-related death events may also be taken into account when deciding to stop randomization.

[Table 1](#) below additionally shows the approximate numbers of randomized subjects needed to observe 161 events based on several other placebo incidence rates.

Table 1: Approximate Number of Subjects Needed to Observe 161 Events

Placebo Incidence Rate	Number of Subjects*
3.0%	6,700
2.75%	7,300
2.5%	8,000
2.25%	9,000
2.0%	10,100
1.5%	13,400
1.25%	16,100
*calculated based on 40% RRR	

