2.4. Definition of Subgroups

Homogeneity of treatment effects, both in HR and direction, will be assessed in the following subgroups classified at baseline and not limited to the following subgroups:

- Age (< 65 vs ≥ 65 ; <75 vs ≥ 75 years)
- Sex (men vs women)
- Race (White vs others)
- Race (White, Black, Asian, others)

- Geographic region (North America, South America, Western Europe, Eastern Europe, other)
- CrCl (≥ 30 to < 50 , ≥ 50 to < 80 , ≥ 80 mL/min)
- Body Mass Index (< 25 , ≥ 25 to < 35 , ≥ 35 kg/m²)
- Admitting diagnosis (HF with reduced ejection fraction (LVEF $\leq 45\%$), acute respiratory insufficiency or acute exacerbation of COPD, acute ischemic stroke, acute infectious disease, and inflammatory diseases)
- History of diabetes (yes vs no)
- History of cancer (yes vs no)
- Baseline D-dimer level ($> 2xULN$ vs $\leq 2xULN$)
- Baseline aspirin use (yes vs no)
- Baseline thienopyridine use (yes vs no)
- Baseline proton pump inhibitor use (yes vs no)
- Duration of index hospitalization (3 to 6, 7 to 10, > 10 days)
- Duration of anticoagulation during index hospitalization (3 to 6, 7 to 10, > 10 days)
- LMWH or UFH during index hospitalization (LMWH vs UFH)
- Use of US approved thromboprophylaxis (ie UFH, enoxaparin and dalteparin) vs other
- Total modified IMPROVE risk factor score (2, 3, ≥ 4)

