6.1. Bleeding Events

Unless otherwise stated, interim and final analyses of the principal safety outcome and non-major clinically relevant bleeding will be based on CEC adjudicated events.

The principal safety outcome is ISTH major bleeding. Treatments will be compared using the same Cox proportional hazards model as that for the primary efficacy outcome described earlier. The analysis will be based on the safety analysis set and on-treatment analysis phase. Treatments will also be compared using Anderson-Gill model for the time to multiple occurrences of the principal safety outcome. The analysis will be based on the safety analysis set and on-treatment analysis phase.

The homogeneity of treatment effects on the first occurrence of the principal safety outcome across subgroups defined in section 2.4 will be examined (at a 2-sided significance level of 0.05) via the test used for the primary efficacy outcome, based on the safety analysis set and on-treatment analysis phase.

Off-treatment major bleeding events, defined by the events from the 3 days after the last dose date, will be summarized by treatment groups.

Other safety outcomes are non-major clinically relevant bleeding and other bleeding.

Non-major clinically relevant bleeding will be analyzed based on time from randomization to the first occurrence. The same analysis as that for the principal safety outcome will be used.

All bleeding, other bleeding, bleeding by BARC classification as well as sub-categories of major bleeding, including critical sites, will be also summarized by treatment groups.

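### SAP 5.2.2 reads a non-significant interaction test as proof of consistency, yet the planned CrCl test would usually miss a complete loss of benefit in the 7.5 mg stratum

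*SAP*

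**What the plan says.** SAP 5.2.2 explores homogeneity of the primary result with a treatment-by-subgroup interaction test at two-sided 0.05, using an unstratified Cox model for CrCl. Its rule for reading the result is "Lack of a significant interaction will imply that the results are consistent across subgroups". The test for a qualitative interaction is run only if the interaction is significant. For each subgroup "the estimate and CI for HR will be constructed", and where a treatment-by-stratum cell has fewer than 5 subjects with the outcome, "interpretation of the CI needs to be done with caution".

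SAP 2.4 lists the CrCl levels as "CrCl (≥ 30 to < 50 , ≥ 50 to < 80 , ≥ 80 mL/min", so the CrCl interaction test has 2 degrees of freedom. SAP 6.1 carries the approach to major bleeding, where homogeneity "will be examined (at a 2-sided significance level of 0.05) via the test used for the primary efficacy outcome". SAP 7 also explores benefit-risk in the same subgroups.

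Protocol 3.2 puts the reduced-dose stratum, CrCl 30 to <50 mL/min, at a share "estimated to be approximately 20% of study population". On the basis of predicted exposure it says that "comparable efficacy and safety would be expected in these 2 population subgroups". Neither document gives the power of any interaction test.

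**The concern.** A non-significant interaction is evidence of consistency only if the test had a good chance of finding a difference that matters. The 161 events were chosen to detect an overall HR of 0.60, not a difference between subgroups, and about one fifth of subjects are in the 7.5 mg stratum.

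The CrCl test is where the trial's own efficacy data meet the protocol's expectation of comparable efficacy at the two doses. Under the rule as written, a weak test that fails to reject would be reported as supporting that expectation.

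The other planned steps do not prevent this. Subgroup HRs and CIs would show the imprecision, but the rule fixes the conclusion whatever they show. The small-cell caution would not be expected to apply: in the equal-risk cases below, the stratum has about 19 to 20 events per arm at 161 events, and 14 to 15 at 120. The qualitative-interaction check is skipped whenever the interaction is missed.

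**Working it through.** **The plan's own figure.** For HR 0.60, two-sided 0.05, 90% power and 1:1 allocation (SAP 1.4), required events = 4 × (1.960 + 1.282)² / (ln 0.60)² = 161.07. This reproduces the plan's 161, and power at 161 events is 90.0%.

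**Inputs.** 161 events, 1:1 allocation and HR 0.60 (SAP 1.4); three CrCl levels (SAP 2.4); 20% of subjects in CrCl 30 to <50 (Protocol 3.2). Assumptions, since the documents are silent: true HR 1.0 in that stratum, one common HR in the two upper levels, and placebo risk in the stratum equal to r times that elsewhere.

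**Formulas.** Placebo events are proportional to subject share × relative risk. Rivaroxaban events = placebo events × HR. Both are scaled to D total events. The variance of the difference in log HR is the sum of 1/events over the four cells (stratum and rest, each by arm). Noncentrality = (ln ratio of HRs)² / variance. Power comes from the noncentral chi-square with 2 df at 0.05.

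To hold the overall effect at 0.60, the HR elsewhere is (0.6 − p)/(1 − p), where p = 0.2r/(0.2r + 0.8) is the stratum's share of placebo events. For r = 1, p = 0.200 and the HR is 0.50; for r = 1.5, p = 0.273 and 0.45; for r = 2, p = 0.333 and 0.40.

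**Worked case, r = 1, HR 0.60 elsewhere.** Events are 19.2 + 19.2 in the stratum and 76.7 + 46.0 elsewhere. SE = √(1/19.2 + 1/19.2 + 1/76.7 + 1/46.0) = 0.373. Noncentrality = (ln(1/0.60)/0.373)² = 1.88. Power is 21.4%, so 78.6% are missed.

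| Placebo risk ratio r | HR elsewhere | Stratum events of 161 | Power, 161 events | Missed | Power, 120 events |
|---|---|---|---|---|---|
| 1 | 0.60 | 38.3 | 21.4% | 78.6% | 16.9% |
| 1 | 0.50 | 40.2 | 37.1% | 62.9% | 28.5% |
| 1.5 | 0.45 | 54.9 | 54.1% | 45.9% | 42.1% |
| 2 | 0.40 | 67.1 | 68.8% | 31.2% | 55.3% |

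The 120-event column is 12,000 × 0.0125 × (1 + 0.6)/2, using the lowest placebo rate in SAP Table 1. It is relevant because SAP 1.4 says "Randomization in this study may be stopped at approximately 12,000 subjects" even if 161 events have not been reached.

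**Sensitivity at 161 events.**
- Using 4/(events) as each group's variance gives 21.7%, 38.1%, 56.6% and 73.0% power for the four rows.
- If the stratum instead has 20% of all events (32.2), power is 19.5% (HR 0.60 elsewhere) and 33.1% (HR 0.50).
- With HR 0.60 elsewhere, power stays below about 29% at any event share.
- A 1-df test of <50 versus ≥50 would miss 72.2% and 53.4% in the two equal-risk cases.
- Simulation (200,000 runs, likelihood-ratio test) gives power of 21.6%, 37.1%, 54.5% and 69.8% for the four rows, and a 5.2% rejection rate with no interaction. How the upper CrCl group is split makes no material difference.
- A reversal is easier to find. With stratum HR 1.5, power is 54–62% with HR 0.60 elsewhere, and about 94% if the overall effect is held at 0.60 under equal risk (HR 0.375 elsewhere).

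**What an apparently perfect result would show.** Suppose the observed ratio of HRs is exactly 1.0, with 32.2 and 128.8 events. SE = √(4/32.2 + 4/128.8) = 0.394, and exp(±1.96 × 0.394) gives a 95% CI of 0.46 to 2.16. That includes 1.0/0.60 = 1.67, which is no benefit in the stratum against the planned effect elsewhere.

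**The case against.** The strongest reply is that little depends on the sentence. The subgroup work is exploratory and sits outside the hierarchy in SAP 5.4. No alpha, primary claim or stopping rule uses it, and a reader would see the 7.5 mg HR with its wide CI beside the stated conclusion. That stands as to weight. It does not make the inference valid: an exploratory test is a poor basis for a prescribed conclusion of consistency.

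Second, the 79% and 63% are unconditional, and a false claim of consistency misleads mainly when the primary succeeds. Success together with a missed interaction occurs in about 53% of trials (HR 0.60 elsewhere, where the overall HR is about 0.68 and the primary succeeds in about 68%) or 56% (HR 0.50). This is a fair qualification, but among successful trials the miss rate is still about 78% and 63%.

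Third, equal placebo risk is not in the documents, and nothing in them predicts HR 1.0 in the stratum; Protocol 3.2 gives reasons to expect the opposite. Both points are true. The scenario is a stress test, and higher stratum risk with the overall effect held at 0.60 lowers the miss rate to about 27–46%.

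Fourth, SAP 6.1 reuses the test without expressly repeating the interpretive sentence, and no power is calculated here for bleeding. That is why only a clarifying cross-reference is asked for there.

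**Conclusion.** The sentence is wrong as written. At 161 events, a stratum with no benefit would be reported as consistent in about 79% of trials (HR 0.60 elsewhere) or 63% (HR 0.50 elsewhere, which holds the overall effect at the planned 0.60). These figures assume 20% of subjects in the stratum, equal placebo risk and the three-level 2-df test. Over all the placebo risks and event shares examined, the range is roughly 27–80%. At 120 events the test is weaker: power is 16–29% with equal placebo risk or a 20% event share, and 42–44% or 55–59% when stratum risk is 1.5 or 2 times higher.

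The consequence is limited to an exploratory reported conclusion. The primary analysis and its type I error are untouched. This should be corrected, but it does not threaten the trial.

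**What to change.** Replace the sentence in SAP 5.2.2 with wording such as: *A non-significant interaction will not be taken as evidence of consistency; consistency will be judged from the subgroup HRs with 95% CIs, with the interaction p-value as supportive.*

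Add one estimate: the ratio of HRs with 95% CI for CrCl 30 to <50 versus ≥50 mL/min, the two CrCl randomisation strata. Ratios for the other subgroups are not required. In SAP 6.1, state that the same interpretation applies to major bleeding.

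The cost is one sentence, one estimate and one cross-reference; subgroup HRs and CIs are already planned. SAP 1 reserves amendments for changes to key analysis methods, so the sponsor may prefer to record this in a dated note. Either way it should be done before unblinding. The change removes the over-claim; it does not give the trial the power to settle the CrCl question.

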5.3. Secondary Efficacy Outcomes

5.3.1. Definition

The secondary efficacy outcomes are the following:

- VTE-related death (death due to PE or death in which PE cannot be ruled out as the cause)
- Symptomatic VTE (lower extremity DVT and non-fatal PE)
- The composite of symptomatic VTE (lower extremity DVT and non-fatal PE) and all-cause mortality (ACM)
- The composite of symptomatic VTE (lower extremity DVT and non-fatal PE), myocardial infarction (MI), non-hemorrhagic stroke and cardiovascular (CV) death (death due to a known CV cause and death in which a CV cause cannot be ruled out; by this definition, a VTE-related death is considered a CV death)
- All-cause mortality (ACM)

